7.0 Study Timelines*

7.1 Each participant with KOA will actively participate in the study eight weeks, depending on the participants scheduling abilities. This will require 10-12 hours total of participation. Participants in the control group are the exception, as they will only be required to attend one session for full participation. This single session will last about 1-2 hours. It is anticipated that it will take approximately 12-18 months to enroll all study participants, with completion of data collection/analyses within this same timeline.

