9.0 Procedures Involved*

9.1 This investigation will be divided into three parts, each associated with one of the specific aims detailed in Section 1. All procedures will be performed in the School of Allied Health Professions, either in the Motion Analysis Laboratory (Gait Lab) or the Rehabilitation Faculty Practice (RFP) Clinic.

Part 1: Compare age and gender matched healthy controls and KOA groups on kinetics, kinematics, and gait speed during self-selected speed via a between groups analysis across the dependent variables, and determine if those differences in the KOA group have a predictive relationship with their KOOS scores.

Part 2: Within-group comparison of both groups (with and without volitional TA activation) and between-groups (control group versus KOA group). Compare pain levels during both conditions via NPRS for the KOA group. Participants will wear biofeedback under both conditions, and all condition trials will be randomized. Alarm or verbal cue will be provided at 30% MVIC, and two electrodes placed over TA/obliquus internus (OI) just medial to anterior superior iliac spine (ASIS). A comparison of TA activation will be performed both within and between groups.

Part 3: Within-groups comparison of KOA group (pre-treatment and post-treatment; six-week training program) on kinetics, kinematics,

PROTOCOL TITLE: The Effects of Core Activation and Stabilization Training on Gait Kinetics, Kinematics, and Speed, and Self-Perceived Function in Patients with Knee Osteoarthritis

and gait speed during self-selected paced ambulation. A comparison of KOOS scores before and after treatment will be performed as well.

9.2 Once recruitment (see 22.0) and informed consent (see 27.0 and 28.0) are completed:

Part 1: All participants will undergo anthropometric data collection first, including weight, height, leg length, knee joint width, and ankle joint width. Age matching will be done within +/- 5 years between the two groups. Reflective markers will then be placed on bilateral lower extremities following the Plug in Gait Model. EMG electrodes will be placed bilaterally just medial to the ASIS, over the TA/OI. The Gait Lab will undergo calibration, and the participant will undergo a static trial. In participants with bilateral KOA, the most painful limb, identified by subjective report, will be used in the data collection procedures. Healthy controls will undergo analysis of their dominant limb by indicating with which leg they would kick a ball.

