than three participants will undergo the training simultaneously. Training sessions will not be performed on consecutive days in an effort to reduce the chances of delayed onset muscle soreness being present during treatment sessions. Additionally, the core training program includes predetermined guidelines on exercise progressions in order to ensure that the exercises are not progressed too rapidly. The PI will be present and will lead all sessions, ensuring that the exercises and their progressions are done correctly.

After the completion of the intervention program, each participant will undergo gait analysis in the same manner mentioned in Part 1, with the exception of no anthropometric data being collected.

Participants will then complete a second, post-intervention KOOS questionnaire, and turn in their home exercise program sheet with tallies from completed sessions. Please see Part 1 for completion of the pre-intervention KOOS questionnaire.

9.3 The table below details the procedures and occurrence of those procedures throughout a single participant's participation in the investigation:

Procedures	Occurrence
Education/Informed Consent	1 all participants
Anthropometric Data Collection	1 all participants
Baseline (Part 1) Without & With Core Activation (Part 2) Pre 6-Week Intervention Gait & EMG Assessment (Part 3)	1 all participants (except no part 3 for controls)
Pain NPRS Assessment	2 for KOA group
Core Stability Intervention Program	12 sessions, plus 18 home program sessions (KOA group only)
Post 6-Week Intervention Gait & EMG Assessment	1 (KOA group only)
Pre and Post 6-Week Intervention KOOS Assessment	2 (KOA group only)

9.4 The exclusion criteria serve to prevent participation of those who require assistance or assistive devices for ambulation, so safety during the ambulation activities is minimized. The adhesive tape used in reflective marker placement is intended for placement on the skin. Regarding PHI, the PI will be the only investigator involved in the recruitment and consent process and will be charged with

PROTOCOL TITLE: The Effects of Core Activation and Stabilization Training on Gait Kinetics, Kinematics, and Speed, and Self-Perceived Function in Patients with Knee Osteoarthritis

protecting the PHI in his office. The motion analysis data and PHI will be protected in the manner discussed in sections 11.3.

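### Weight is not recorded at the post-training gait session and the scaling of F2 and KAM is not stated, so weight change cannot be separated from a training effect in these two outcomes

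*Combined protocol and SAP*

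**What the plan says.** Section 9.2, Part 1 sets the baseline measurements: "All participants will undergo anthropometric data collection first, including weight, height, leg length, knee joint width, and ankle joint width". The same paragraph adds "The Gait Lab will undergo calibration, and the participant will undergo a static trial", without saying whether the participant stands on a force plate.

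For the session after training, section 9.2, Part 3 states that "each participant will undergo gait analysis in the same manner mentioned in Part 1, with the exception of no anthropometric data being collected". The table in section 9.3 agrees: the row "Anthropometric Data Collection" has one occurrence, for all participants. The omission is therefore explicit and consistent.

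Section 9.1 describes Part 3 as a "Within-groups comparison of KOA group (pre-treatment and post-treatment; six-week training program"), so each person is compared with their own baseline and there is no untrained knee osteoarthritis group. Section 7.1 gives the time frame: "Each participant with KOA will actively participate in the study eight weeks". F2 and KAM are two of the five gait outcomes under Specific Aim 3.

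Section 11.1 contains the only adjustment for body size. BMI becomes a covariate in the kinetic and kinematic analysis if mean BMI differs significantly between the two groups. No section states whether F2 or KAM is expressed in absolute units or relative to body weight.

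**The concern.** F2 is a force and KAM is a moment, and both rise and fall with body weight. If a participant's weight changes between sessions while the gait pattern does not, the recorded value can still change. To tell these apart, the analyst needs the weight on the day of the second session, and that is among the measurements the plan drops.

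Nothing else in the plan covers the gap. The BMI rule is triggered by a difference between groups and does not address change within the knee osteoarthritis group. With no untrained comparator, an average weight shift would be read as part of the training effect. The third hypothesis of Aim 3 regresses change in these outcomes on sessions completed. If people who complete more sessions also change weight more, that regression is affected too.

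Two of the five Part 3 gait outcomes are exposed. Time to first peak force, knee flexion angle and gait speed do not scale directly with weight, nor does the KOOS.

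**Working it through.** **The plan's own figure.** Section 11.2 requires 45 participants and assumes 10% attrition: 45 / 0.9 = 50, which matches the 50 stated. The 45 cannot be reproduced because alpha, power, effect sizes and SDs are not given. Applying the same attrition to the 25 recruits with knee osteoarthritis gives 25 × 0.9 = 22.5, taken as 22 completers.

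**Effect of weight change on F2.** Let f be F2 per unit of body weight, unchanged between sessions. Let weight go from W to W(1 + w). Then:

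- Raw F2 goes from fW to fW(1 + w), a relative change of w.
- F2 divided by baseline weight goes from f to f(1 + w), a relative change of w.
- F2 divided by same-session weight stays at f, a change of 0.

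A 1%, 2% or 3% weight change therefore moves F2 by 1%, 2% or 3% under either of the first two scalings. KAM moves in the same direction, but exact proportionality is shown here only for F2.

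**Loss of precision.** The documents give no SD for weight change or for outcome change, so all values here are assumptions. Weight change is taken as independent of gait change. The true effect is set to give 80% power in a two-sided paired t-test at alpha 0.05 with n = 22, which needs a standardised effect dz = 0.626. With weight-change SD s_w and outcome-change SD s_F, both in percent, the variance is multiplied by 1 + (s_w / s_F)² and dz is divided by its square root.

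| s_F | s_w | Added variance | dz | Power |
|---|---|---|---|---|
| 3% | 1% | 11.1% | 0.594 | 75.7% |
| 3% | 2% | 44.4% | 0.521 | 64.5% |
| 3% | 3% | 100% | 0.443 | 50.9% |
| 5% | 1% | 4.0% | 0.614 | 78.4% |
| 5% | 2% | 16.0% | 0.582 | 73.9% |
| 5% | 3% | 36.0% | 0.537 | 67.1% |
| 8% | 1% | 1.6% | 0.622 | 79.4% |
| 8% | 2% | 6.2% | 0.608 | 77.6% |
| 8% | 3% | 14.1% | 0.587 | 74.7% |
| 20% | 1% | 0.3% | 0.626 | 79.9% |
| 20% | 2% | 1.0% | 0.623 | 79.6% |
| 20% | 3% | 2.2% | 0.619 | 79.1% |

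With a Bonferroni alpha of 0.05 / 5 = 0.01 and the effect reset to give 80% power (dz = 0.792), the two rows with s_F = 5% and s_w of 1% and 2% become 78.1% and 72.5%.

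**Possible bias.** Suppose mean weight changes by 1% (SD 2%) and gait does not change. The probability of a significant result in that direction, nominally 2.5%, depends on s_F:

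- s_F = 5%: total SD = √(25 + 4) = 5.39, dz = 1 / 5.39 = 0.186, probability about 13%.
- s_F = 8%: total SD = √(64 + 4) = 8.25, dz = 0.121, probability about 8%.
- s_F = 20%: total SD = √(400 + 4) = 20.1, dz = 0.050, probability about 4%.

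**The case against.** The strongest objection is that the documents never say baseline weight will be reused. A reader might infer from the omission that every weight change enters F2 and KAM as measurement error. That goes too far, because it needs a scaling rule the plan does not give. A force plate records raw force without any weight input. If weight falls and raw F2 falls with it, the measurement is correct and the load has really changed. Section 2.3 is concerned with wear on osteoarthritic joints, so absolute load could be a legitimate target. This stands: in raw units the problem is confounding, not error.

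The weight may also be recoverable. The second session repeats the Part 1 gait procedure, which includes a static trial. The lab has two embedded force plates (section 20.2), and all force-plate data are kept (section 10.2). This also stands as a possibility. However, no section says that the static trial is on a plate or that weight is taken from it, and the explicit exclusion of anthropometric data points the other way.

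A reader might also infer that participants will lose weight on average and so bias the result. The documents describe a core exercise programme with no dietary or weight-loss component and predict no weight change. Bias is possible but not shown.

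Finally, the size rests wholly on assumed inputs. The large losses in the table need a large weight-change SD together with a small outcome-change SD, and nothing in the documents supports using one outcome SD for both F2 and KAM. This is correct, and it limits the weight of the point.

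**Conclusion.** The concern holds in a limited form. The plan expressly leaves weight out of the post-training session and does not state the normalisation of F2 and KAM. Unless weight is obtained by a route the plan does not mention, weight change within the knee osteoarthritis group is either scaling error or a load change that cannot be told apart from a gait effect.

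The consequence is probably modest. At an assumed outcome-change SD of 5%, power falls from 80% to 78.4% or 73.9% for weight-change SDs of 1% or 2%. At an outcome-change SD of 20%, which is possible for KAM, the loss is under one percentage point. The documents give none of the SDs behind these figures. This is an inexpensive improvement and not a threat to the study as a whole. It is still worth making before data collection, because a weight not recorded at that visit cannot be reliably recovered later.

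**What to change.** In section 9.2, Part 3 and the section 9.3 table, add body weight to the post-training gait session for the knee osteoarthritis group. Use the body weight scale already among the listed equipment (section 9.4), or specify that weight is taken from a static trial on a force plate at both sessions. In section 11.1, state that F2 and KAM are normalised to the weight from the same session. If absolute load is also of interest, report it separately with the weight change alongside. Height, leg length and joint widths can stay as measured at baseline.

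The cost is about one minute per participant with knee osteoarthritis, with no new equipment and no extra visit.

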10.0 Data and Specimen Banking*

- 10.1 A repository will be used to store all of the gait kinetic, kinematic, and speed data collected during the motion analysis sessions. This data will be stored on the computer system in the Gait Lab which is password protected, in addition to the lab itself being key access. The Data Collection Form (see attached), in addition to completed Core Program Tracker for Investigator Use and KOOS forms (see attached) will be included in the repository. This data will be kept in the PI's office which is key access, with the Data Collection Form staying on the PI's password protected personal laptop or state desktop computer, with the hardcopy KOOS and Core Program Tracker for Investigator Use forms will remain in the hardcopy compliance binders. The data will be stored for a period of seven years. Persons using the Gait Lab will have access to this data but will require IRB approval for use in research activities.
- 10.2 The repository data will include all force plate data and that collected from the infrared cameras, including pelvis, hip, knee, and ankle joint moments, range of motion in all three planes, and spatiotemporal gait characteristics, in addition to anthropometric data, KOOS scores, pain NPRS ratings, and exercise data from the Core Program Tracker for Investigator Use form.
- 10.3 In order for the data to be accessed for research purposes, a new approved IRB protocol will be required. Additionally, if the author

PROTOCOL TITLE: The Effects of Core Activation and Stabilization Training on Gait Kinetics, Kinematics, and Speed, and Self-Perceived Function in Patients with Knee Osteoarthritis

of said protocol is not the PI or the sub-investigator, they will need to request permission from one of these investigators prior to including this request in their proposed research protocol.

11.0 Data Management* and Confidentiality

- 11.1 Data analysis will be performed by the PI, with the assistance of the sub-investigator. The PI will use the latest version of SPSS available to the PI on his personal laptop computer (see 11.3 for security details). The kinetic, kinematic, and speed data will be analyzed together, either by a MANOVA (if assumptions are met) or separate ANOVA/mean comparison analyses with Bonferroni corrections, while the pain NPRS and KOOS scores will be analyzed each individually via means comparisons. The EMG data will be analyzed via a 2x2 ANOVA or separate means comparisons. If the groups have significantly different mean BMIs, then it will be included in the kinetic and kinematic analysis as a covariate. The predictive relationship between the number of exercise sessions and the change observed within the KOA group for each variable will be analyzed via regression analysis.
- 11.2 An *a priori* power analysis was performed to determine the number of participants required to achieve significance for the variables of highest interest in the investigation. Data from previous publications on these variables were used in the power analysis. These include the following: T₁ between¹⁶ and within ([name], [name], unpublished data, May 2018) groups, F₂ between and within groups,¹⁸ KAM between and within groups,¹⁷ KFA between¹⁴ and within²⁶ groups, and gait speed between¹⁶ and within²⁷ groups for the kinetic and kinematic analyses. Additionally, the KOOS²⁸ was examined for within-group means comparison. The PI used G*Power (Heinrich-Heine-University Düsseldorf, Düsseldorf, Germany) for the purposes of these analyses. It was determined that 45 participants would be required, except for the KFA which would require a larger sample size. Since this variable will be collected concurrently along with the other kinetic and kinematic data, and all the other variables of interest are appropriately powered at a much lower sample size, we felt confident proceeding regardless of being underpowered for one of these five dependent kinetic/kinematic variables of interest.

Since this study involves a six-week intervention, an attrition rate of 10% was assumed, so a total of 50 participants (25 healthy controls and 25 with KOA) will be recruited. Data analysis will be completed

PROTOCOL TITLE: The Effects of Core Activation and Stabilization Training on Gait Kinetics, Kinematics, and Speed, and Self-Perceived Function in Patients with Knee Osteoarthritis

intermittently throughout data collection, and if significance is achieved prior to 50 participants completing their participation, recruitment will be discontinued, and only those in the study will be allowed to complete the study. This will be done in an effort to reduce the number of people undergoing this less than minimal risk investigation.

- 11.3 The kinetic and kinematic data will be stored on the computer system in the Gait Lab. This lab is key accessible by the faculty of the SAHP. The computer system is password protected, with the PI and the sub-investigator being the only two individuals who currently know that password. Other faculty members would need to get the password from these two investigators for their own research activities unrelated to this investigation. The data will be backed up on an external hard drive belonging to the two investigators. No personal identifying information will be included in this data, as the participants will be identified by their participant identification numbers. The key to these identifiers will be the signed consent forms maintained by the PI that have both the participants' names and identification number on them. These forms will be maintained in the PI's office (SAHP Rm 2-234) which is key access, in a compliance binder. The data collection forms and KOOS questionnaires will also be located in this binder, with only the identification number on them. All of the deidentified raw data, including kinetic, kinematic, gait speed, NPRS ratings, and KOOS scores will also be maintained on the PI's personal laptop and work desktop computers for the purposes of data analysis, and preparations for dissemination after the completion of the data collection and analysis. Both of these computers are password protected. This de-identified data will be backed-up on the PI's personal flash drives.
- 11.4 The PI and/or the sub-investigator will be performing a calibration of the motion analysis system prior to each data collection session, thereby reducing the risk of errors in the data from loss of calibration over time. EMG calibration and set-up will be completed by the sub-investigator. Additionally, the PI will be providing the same instructions on the core activations and pain NPRS reporting performed during Part 2 of the investigation.
- 11.5 See 11.3 regarding the mode and length of data storage, and who will have access to the data.

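### If the gait variables are tested separately, section 11.1 uses single-step Bonferroni; Holm's step-down would never reject less at the same family-wise error, with a gain of about 0 to 13 points for most variables that depends on unstated assumptions

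*Combined protocol and SAP*

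**What the plan says.** Section 11.1 analyses the kinetic, kinematic and speed data jointly by MANOVA when its assumptions are met. The alternative is "separate ANOVA/mean comparison analyses with Bonferroni corrections". The divisor is not given, and no step-down method is mentioned.

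Section 11.2 counts five variables: T1, F2, KAM, KFA and gait speed. On sample size it states "It was determined that 45 participants would be required, except for the KFA which would require a larger sample size", and the investigators accept being "underpowered for one of these five dependent kinetic/kinematic variables of interest". It adds that "an attrition rate of 10% was assumed", and that "a total of 50 participants (25 healthy controls and 25 with KOA) will be recruited". It also provides for data to be analysed from time to time during collection, with recruitment ending early once significance is reached. No adjustment for those looks is stated.

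H1 of each of the three aims (section 1.2) covers all five variables. H2 of Aim 1 then takes the gait differences found significant and relates them to KOOS.

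**The concern.** Single-step Bonferroni holds every variable to the same strict threshold whatever the other four show. Holm relaxes the threshold for the remaining variables after each rejection, without any further assumption. When several effects are real, which is what H1 of each aim proposes, Bonferroni can miss a variable that Holm would declare, for no benefit in error control.

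Two features make this relevant here. The study is small, with about 22 KOA completers after attrition, and it concedes low power for KFA. In addition, the list of significant variables from Aim 1 feeds the KOOS prediction, so a missed variable drops out of a later analysis as well.

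**Working it through.** **The plan's own figure.** 45 / (1 − 0.10) = 50, as stated. The 45 itself cannot be rebuilt, because alpha, target power, effect sizes and SDs are not given.

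**Assumed inputs.** Two-sided tests; family-wise alpha 0.05; five variables; 22 vs 23 for between-group tests (from 45) and 22 for within-KOA tests (25 × 0.9 = 22.5); equal correlation between variables from 0 to 0.8.

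**The two rules.** Bonferroni compares every p-value with 0.05/5 = 0.01. Holm orders the p-values and compares the smallest with 0.05/5 = 0.01, then 0.05/4 = 0.0125, 0.05/3 = 0.0167, 0.05/2 = 0.025 and 0.05, stopping at the first failure. Three facts follow without simulation:
- The first step is the same, so the chance of at least one rejection is identical.
- Every later threshold is at least 0.01, so Holm rejects whatever Bonferroni rejects.
- No threshold exceeds 0.05, so no variable can gain more power than its own unadjusted test at 0.05.

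**Starting point under Bonferroni.** For two groups, the noncentrality is d × √(n1·n2/(n1+n2)). With d = 0.855 this is 0.855 × √(22 × 23/45) = 2.87 on 43 degrees of freedom. Power is 80% at 0.05 and 57% at 0.01. For a paired test with n = 22 and 80% power at 0.05, power at 0.01 is 55%.

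**Gain, Holm minus Bonferroni, in percentage points.** Simulation of 40,000 trials per scenario; each range runs over correlations 0 to 0.8. The percentage in each row is single-test power at 0.05 unless noted.

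| Pattern | Variables with the main effect | KFA |
|---|---|---|
| One real effect at 80%, four null | 0.0–0.1 | – |
| Two real at 80%, three null | 1.6–2.2 | – |
| Three real at 80%, two null | 3.6–4.5 | – |
| Four at 80%, KFA null | 6.0–7.6 | – |
| Four at 80%, KFA 30% | 5.9–8.8 | 8.6–16.3 |
| Four at 80%, KFA 50% | 6.4–9.9 | 11.9–18.7 |
| Four at 90%, KFA 50% | 5.7–9.9 | 16.6–22.5 |
| Four at 80% at alpha 0.01, KFA 50% | 4.7–8.7 | 19.0–23.3 |
| All five at 50% | 3.8–6.5 | same |
| All five at 80% | 9.0–12.3 | same |
| All five at 90% | 7.9–12.9 | same |
| All five at 80%, paired, n = 22 | 9.7–13.0 | same |

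Simulated family-wise error with all five null was 0.032 to 0.049 for each method.

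**Named effect sizes, paired, n = 22, correlation 0.3.** With four effects of 0.63 SD and KFA at 0.3 SD, power on the four goes from 56% to about 64–65%. At 0.79 SD it goes from 80% to 87%. In these two cases KFA goes from about 10% to 20–25%. With four effects of 1.0 SD the move is only from 96% to 98%, because little power is left to gain.

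**Repeated looks.** The plan gives no schedule, so I assumed five looks, at 8, 12, 16, 19 and 22 participants. The setting is paired, correlation 0.3, four real effects and KFA null, counting a rejection at any look. The chance of falsely rejecting KFA is:
- effects 0.63 SD: Bonferroni 3.1%, Holm 5.9%
- effects 0.79 SD: Bonferroni 3.0%, Holm 7.8%
- effects 1.0 SD: Bonferroni 3.0%, Holm 9.8%

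With all five variables null, both methods reach about 13.6% for any false rejection.

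**The case against.** Bonferroni is a legitimate correction and the plan contradicts nothing by choosing it. A reader might infer that section 11.1 contains a statistical error. It does not: the choice is conservative, not invalid, and it applies only if the MANOVA route is dropped. The documents give no reason to expect that. This objection stands and limits the point to an efficiency improvement.

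A reader might also infer a fixed benefit, such as seven or eight points of power on each variable. The documents do not support that. They give none of the quantities that determine the gain, and the gain is not uniform across variables. It nearly vanishes if one or two effects are real, and shrinks if the effects are very large. Section 11.2 says the variables other than KFA are adequately powered with far fewer participants, so a starting power near 56% may be too pessimistic. Without the alpha used, this cannot be settled.

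Nor does Holm cure the conceded KFA shortfall. In the paired example KFA still reaches only 20–25%, and its power is capped at that of its unadjusted test.

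The weightiest objection is that equal error control presumes valid p-values from one analysis. Under the stopping rule in section 11.2 neither method has its guarantee, and in the assumed example Holm takes the false rejection rate of a null KFA above 5% while Bonferroni stays near 3%. This is no case for Bonferroni as such, since it too fails when all five variables are null. It does mean the looks must be dealt with alongside the change.

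**Conclusion.** The point holds as a low-cost improvement to the separate-test route. That Holm never rejects less, at the same family-wise error in a single analysis, is a mathematical fact and needs no assumption about this trial.

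The size is conditional on two-sided tests, family-wise 0.05, a family of five and the assumed effects and correlations. The gain per variable is about 0, 2 or 4 points with one, two or three real effects. It is roughly 6 to 10 on the four main variables when KFA is weaker or null, falling to about 5 or below when those effects are large. It is up to about 13 when all five are similar. A weak KFA could gain up to about 23 points and remain underpowered. The benefit lies entirely in the second and later variables declared. The claim of equal error control does not extend to the plan's unadjusted intermittent analyses.

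**What to change.** In section 11.1, replace 'Bonferroni corrections' with 'Holm step-down correction across the five gait variables within each comparison', and state that it applies to a single final analysis. This wording also settles the correction family, which section 11.1 leaves open. The investigators should confirm that they intend the five variables within each comparison, and not a family pooled over the between-group, activation and pre/post comparisons.

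The change costs a few words and no participants, and adjusted p-values can be worked out by hand from standard output. It should be made before results are seen, because a later switch would look selective.

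There are two downsides. Simultaneous confidence intervals are less simple under Holm, though Bonferroni-width intervals can be kept for display. And the change should not be made in isolation: the unadjusted looks with stopping on significance in section 11.2 must be removed or given a proper adjustment, since otherwise Holm is more exposed than Bonferroni to a false claim on a null variable when the others are real.
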